Study Protocol and Statistical Analysis Plan

Investigating Hearing Aid Frequency Response Curves – ID#3167

July 24, 2024

NCT05521308

Investigating Hearing Aid Frequency Response Curves – ID#3167

1 Objectives and hypotheses of the clinical investigation

1.1 Purpose of the clinical investigation claims for clinical performance, effectiveness or safety of the investigational device that are to be verified

The study is an exploratory study in which we are evaluating various frequency gain curves for streaming and acoustic programs. Participants will be asked to rate overall preference while streaming and overall program preference in the presence of live stimuli. This clinical investigation is being conducted to determine if it is beneficial to implement new frequency gain curves for our products.

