1.2 Primary and Secondary Objectives

Primary Objective

Determine if applying frequency specific gain changes to our current streaming programs are preferred by hearing aid users when compared to our current streaming program.

Secondary Objectives

- Determine if applying frequency specific gain changes to our current acoustic programs are preferred by hearing aid users when compared to our current acoustic programs.
- Determine if a proposed frequency response curves will impact speech intelligibility when compared to our current frequency response curves.

2 Design of the clinical investigation

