2.1 General

2.1.1 Design Type

This clinical investigation is an interventional study and conducted at one investigation site. The investigation consists of a single group of participants that will be tested in all conditions (cross-over). When doing the streaming task, both the participant and the investigator will be blinded to the gain curves that are being compared as the software will randomize this. During the live preference ratings, participant's will be blinded to the program they are under, however the investigator will know the program as they will program the hearing aids prior to testing.

There are three gain curves that will be tested for the streaming task (Variations #1, #2, and #3) and two gain curves (Standard curve and Variation #4) that will be tested for live ratings task. Please note that changing between frequency curves is done simply by clicking a button on the hearing aid or via a mobile app. This will be done for the US matrix test and the live sound quality ratings task. For the streaming sound quality task, participants will compare pre-recorded stimuli, which have the various gain curves applied, via hearing aids. Frequency curves (i.e., interventions) can be toggled back and forth via the ratings software. Therefore, multiple gain curves (i.e. interventions) are compared simultaneously in each task (outcome measure) and participants can go back and forth between interventions during a task. This is done to allow participants to make accurate preference selections when comparing the various curves. The US matrix test is the only task in which switching back and forth during a measurement is not allowed

as it is an objective measure of speech recognition and SRT50 scores are recorded per condition tested (unaided, standard curve, and variation #4). Switching will only occur between measurements for the US Matrix test task.

Streaming Program Interventions
Variation #1
Variation #2
Variation #3
Acoustic Program and US Matrix Test Interventions
Standard Curve
Variation #4

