3.1 Determination of Sample Size

We will recruit 25 participants for all tasks. To obtain a power of 90% with 10% of risk of running into beta error (i.e., miss) and with 5% risk of running into alpha error (i.e. false alarm), the power analysis estimated the total sample size to be 25, leading to an actual power of 90%.

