3.3.2 Primary Endpoint Analysis

The primary analysis will be the subjective ratings participants provide for the streaming task. Subjective ratings will be tallied to see which frequency response curve was preferred the most. Participants will be presented with two samples at a time and will choose which sample they prefer. For example, if Sample A was preferred over Sample B, then Sample A gets a score of 1. If Sample B was preferred over Sample A, then Sample B gets a score of 1. In some trials, if the participant does not notice a difference between the two samples, then neither sample will get a score. At the end of the task, scores will be tallied to determine which sample was preferred the most overall. There will be 3 different samples. The minimum value for the tallied score would be 0 (the sample was not preferred at all) and the maximum value would be 2 (implying that the sample was preferred in all trials in which it was involved). Higher scores mean that the sample was preferred more and lower scores mean the sample was not preferred as much when compared to the other samples.

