3.3.3 Secondary Endpoint Analysis

The secondary analysis will consist of evaluating the subjective ratings for the acoustic tasks and the objective scores for the speech in noise test. Live preference ratings will be done in a similar fashion to the streamed preference ratings, however there will only be two programs to compare. Participants will do a live paired comparison task and determine which frequency response curve they prefer when listening to various sound samples. At the end, preferences will be tallied to determine which program was preferred overall. Additionally, these ratings will be done in the sound booth as well as outside.

For the speech test, average scores across all participants will be compared to determine equivalence. Lower scores will indicate better performance.

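### The plan claims 5% alpha and 90% power at N = 25, but both preference endpoints are decided by a highest-tally rule with no test, so neither figure describes the planned analysis

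*Combined protocol and SAP*

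**What the plan says.** **Sample size (Section 3.1).** The plan sets 25 participants for every task, with alpha 5% and beta 10%, and reports that "the power analysis estimated the total sample size to be 25, leading to an actual power of 90" per cent. It gives no test, endpoint, effect size, variability, preference rate or sidedness.

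**Primary analysis (Section 3.3.2).** Three streaming curves are compared in pairs. The preferred one scores 1, and "if the participant does not notice a difference between the two samples, then neither sample will get a score". Each curve's score runs from 0 to 2. The analysis ends there: "At the end of the task, scores will be tallied to determine which sample was preferred the most overall".

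**Live task (Section 3.3.3).** Two programs are compared in the booth and outside: "At the end, preferences will be tallied to determine which program was preferred overall".

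**Objective and comparator (Sections 1.2 and 2.1.1).** The primary objective asks whether changed curves are "preferred by hearing aid users when compared to our current streaming program". The design section says "There are three gain curves that will be tested for the streaming task (Variations #1, #2, and #3"), and a standard curve is listed only for the acoustic and US Matrix tasks.

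**Purpose (Section 1.1).** The study is called exploratory, but it is also "being conducted to determine if it is beneficial to implement new frequency gain curves for our products".

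**The concern.** Alpha and power belong to a decision rule that can fail to reject a stated null hypothesis. The tally has no such outcome. Except for an exact tie at the top, it always names a winner, whether the lead is one point or thirty. The 5% and 90% in Section 3.1 therefore have nothing to attach to in Sections 3.3.2 and 3.3.3.

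This matters because Section 1.1 links the study to the question of adopting new gain curves. A reader who sees a 5% false-alarm risk in the sample-size section may well apply it to the winning curve, although chance alone usually produces a winner.

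A related gap stands in the way of a repair. The primary objective is a comparison with the current streaming program, and the plan does not say which of Variations #1–#3, if any, is that program. Until it does, a test of the primary objective cannot be written.

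**Working it through.** **Inputs from the documents.** n = 25, alpha 5%, power 90% (Section 3.1); three streaming curves scored 0–2, with a 'no difference' option (Section 3.3.2); two live programs (Section 3.3.3). A maximum score of 2 with three curves implies three pairs, each judged once per participant.

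**Assumptions.** The documents give neither the share q of 'no difference' answers nor, for the live task, the number of sound samples, so ranges are used. Judgements are taken as independent unless stated otherwise.

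**1. Can N = 25 be reproduced?** No: no effect or test is given. Solving backwards for the effect that gives 90% power at n = 25:

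- Paired t-test: standardized difference 0.68 two-sided, 0.60 one-sided.
- Exact two-sided sign test: true preference about 80%.
- Three-level repeated-measures ANOVA: f from 0.23 (correlation 0.7) to 0.42 (correlation 0).

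Other effects give other sizes; a paired difference of 0.5, for instance, needs 44 participants two-sided. N = 25 is neither confirmed nor refuted.

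**2. What the streaming tally does with no true preference.** For each pair, the 25 answers are multinomial with probabilities (1−q)/2, (1−q)/2 and q. Each curve's total is the sum of its wins over its two pairs. Simulation, 400,000 runs:

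| 'No difference' (q) | Sole winner |
|---|---|
| 0% | 91% |
| 20% | 90% |
| 40% | 89% |
| 60% | 87% |
| 80% | 82% |
| 90% | 76% |
| 100% | 0% |

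At q = 0–40% the median chance lead of first over second is 3 points, and the 95th percentile is 8–9. If each participant instead ranks the three curves consistently, with no ties, a sole winner appears in 92% of trials and the 95th percentile of the lead is 11. If pairs are repeated over 2–8 recordings, the sole-winner rate is 92–97% at q = 0–40%, so the one-judgement reading does not drive the result.

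**3. The directional error.** The sole-winner rate counts any curve. If one of the three is the current program (an assumption), the error relevant to the primary objective is a changed curve out-scoring it by chance. At q = 0–40% this happens in about 63% of trials, and a changed curve is sole winner in 59–61%.

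**4. Live task, no true preference.** With one choice per participant, P(Variation #4 wins) = P(X ≥ 13 | 25, 0.5) = 50% with no ties, and about 45% at q = 40%. Over 1–8 sound samples and q = 0–40%, some program wins in 89–100% of trials and Variation #4 in 44–50%. A 13–12 result counts as a win, yet its exact 95% interval is 31–72%.

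**5. What 25 participants could detect with a test.** Exact two-sided sign test, P(X ≥ c | n, p) = 0.90 solved for p:

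| Informative answers | Level | Reject at c or more | Preference for 90% power |
|---|---|---|---|
| 25 | 5% (actual 4.3%) | 18 | 80% |
| 25 | adjusted for 2–3 comparisons | 19 | 84% |
| 20 | 5% | 15 | 83% |
| 20 | adjusted for 2–3 comparisons | 16 | 87% |

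Friedman test on the 0–2 scores, one curve favoured over both others: 90% power at a preference of about 74–75% with no ties, 79% with 20% ties and 85–86% with 40% ties.

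**The case against.** **The study is exploratory.** A descriptive tally is a legitimate summary in exploratory preference work, and Section 1.1 does not say that the winner will be implemented. That stands. The fault is to pair the tally with a 5%/90% justification, and removing that sentence is an acceptable minimal repair.

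**The 87–91% figure is not a false-alarm rate.** It includes wins by the current program, if that is among the three. This is correct, and 91% should not be set directly against 5%. The directional figure of about 63% is the fairer comparison, but it assumes that one curve is the current program. If none is, a sole winner is not an error against the stated objective; the tally then simply does not address that objective.

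**A selection rule does have calculable properties.** With one curve favoured over both others and no ties, the tally picks it in 80% of trials at a 60% preference and 94% at 65%. That is also true. But such a figure needs an assumed effect, which Section 3.1 does not state, and it brings no control of false positives.

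**The power claim might belong to the speech test.** Section 3.1 covers all tasks, and Section 3.3.3 compares average speech scores for equivalence. That comparison has no named test and no margin either, and Section 3.1 does not refer to it, so it does not rescue the claim.

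**Conclusion.** The concern holds. The stated 5% alpha and 90% power are not properties of the planned analysis of either preference endpoint, and no other section supplies a test to which they could apply. Under no true preference, the streaming tally names a sole winner in 87–91% of trials at 0–60% 'no difference' answers. If one curve is the current program, a changed curve beats it by chance in about 63% at 0–40%. Variation #4 wins the live task by chance in 44–50%.

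The exact percentages rest on assumed tie rates, numbers of repeats and independence of judgements. The conclusion does not, short of nearly all answers being 'no difference'. N = 25 is not shown to be wrong; it is unsupported. The point should be settled before analysis, since it affects the primary endpoint and the only sample-size justification.

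**What to change.** **Preferred, because Section 1.1 links the result to an adoption decision:**

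1. **Section 3.3.2.** State which streaming curve is the current program, or that none is, and how many judgements each pair receives. Keep the tally as description. Add a participant-level test: for example, a Friedman test on the 0–2 scores, then Holm-adjusted exact sign tests, limited to comparisons with the current program if it is one of the three. Say that 'no difference' answers are left out of the sign tests and reported as a count. Give preference proportions with exact 95% confidence intervals. If pairs are repeated, reduce to one score per participant first. If none of the three is the current program, these tests compare the variations only with one another, and the objective in Section 1.2 and the comparison must be reconciled.
2. **Section 3.3.3.** For the live task, use one score per participant for each setting (booth, outside), a sign test, and the proportion with its interval.
3. **Section 3.1.** Restate power for the chosen test and its assumed effect. For example: with 25 informative answers, an exact two-sided sign test has 90% power if about 80% prefer one curve (84% after adjustment).

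**Minimal alternative, if the study is to stay purely exploratory:** delete the alpha and power sentence from Section 3.1, report the tally with proportions and 95% confidence intervals, and declare no winner.

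**Cost.** Wording and a few lines of analysis, with no change to the visits or the number of participants. The listening task is also unchanged, unless the current program turns out not to be among the three curves and has to be added. The stated power becomes less favourable, and under the minimal alternative no winner can be claimed.

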3.3.3 Secondary Endpoint Analysis

The secondary analysis will consist of evaluating the subjective ratings for the acoustic tasks and the objective scores for the speech in noise test. Live preference ratings will be done in a similar fashion to the streamed preference ratings, however there will only be two programs to compare. Participants will do a live paired comparison task and determine which frequency response curve they prefer when listening to various sound samples. At the end, preferences will be tallied to determine which program was preferred overall. Additionally, these ratings will be done in the sound booth as well as outside.

For the speech test, average scores across all participants will be compared to determine equivalence. Lower scores will indicate better performance.

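### The live preference endpoint is reduced to one overall tally, with no result by environment, no listener-level summary and no measure of uncertainty

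*Combined protocol and SAP*

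**What the plan says.** Section 3.3.3 (Secondary Endpoint Analysis) holds the whole analysis plan for the live ratings. Participants make paired comparisons of two programs and "determine which frequency response curve they prefer when listening to various sound samples". The summary is that "preferences will be tallied to determine which program was preferred overall". The next sentence reads "Additionally, these ratings will be done in the sound booth as well as outside".

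The section describes the task as similar to the streaming task. Section 3.3.2 scores that task at one point for each preferred choice, and at nothing for either sample when no difference is noticed.

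Section 2.1.1 gives a single group tested in every condition, with Standard and Variation #4 as the two live programs. Section 3.1 sets the size: "We will recruit 25 participants for all tasks".

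For the live ratings, the plan does not give the number of sound samples, a count by sample or by environment, a listener-level step, or any test, interval or model.

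**The concern.** Each listener contributes several choices, made on different samples and in two settings. The only output named is one program preferred overall. Three things follow.

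- **Masking.** If preference depends on the setting or the sample, one tally averages the difference away. Section 1.1 says the study is to inform whether new gain curves are worth implementing in products, and a preference that reverses between settings bears directly on that decision. The sponsor collects ratings in both settings, but the plan gives no way to use the contrast.
- **Chance.** A tally always ranks the programs unless they tie exactly. Without an interval or test, a small lead cannot be told from no preference.
- **Unit of evidence.** Choices by one listener are likely to be correlated. The independent units are 25 people, not 25 times the number of choices. Anyone who later attaches a p-value to the raw count would overstate its precision.

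**Working it through.** **The plan's own figure.** Section 3.1 states that "the power analysis estimated the total sample size to be 25", for 90% power and a 5% alpha error. It gives no effect size, preference rate, test or sidedness, so 25 can only be back-solved. It fits, for example, a paired t-test with a standardised difference of 0.68 (two-sided), or an exact sign test with a true preference of about 80%. The figure is neither confirmed nor refuted. What matters here is that the study is sized in participants.

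**Step 1: masking (arithmetic only).** Suppose each of the 25 listeners gives one net choice per environment.

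- Booth: 18/25 for Variation #4; exact two-sided sign test p = 0.043.
- Outside: 7/25; p = 0.043 in the other direction.
- Sum: 18 + 7 = 25 of 25 + 25 = 50; p = 1.0.

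A stronger reversal, 20/25 and 5/25 (p = 0.004 each), also sums to 25/50. The split is illustrative. A partial reversal hides less: 20/25 and 8/25 (p = 0.004 and p = 0.11) sum to 28/50 (p = 0.48).

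**Step 2: chance.** With one result per listener and no ties, 25 is odd, so one program must lead. If the true preference is 50%, a split of 15 to 10 or wider in either direction has probability 2 × P(X ≥ 15) = 0.42, where X is binomial(25, 0.5). An exact two-sided 5% sign test needs at least 18 of 25 (actual level 4.3%).

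**Step 3: repeated choices (assumed inputs).** Let m be the number of judgments per listener over both settings, and ICC the within-listener correlation. The plan gives neither, so both are varied. The design effect is DE = 1 + (m − 1) × ICC.

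- m = 4, ICC = 0.2: DE = 1 + 3 × 0.2 = 1.6.
- m = 8, ICC = 0.5: DE = 1 + 7 × 0.5 = 4.5.
- m = 6, ICC = 0.3: DE = 1 + 5 × 0.3 = 2.5, so 25 × 6 = 150 choices carry the information of 150 / 2.5 = 60.

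The table gives the true type I error if the raw count were tested with an exact two-sided 5% binomial test as though choices were independent (beta-binomial simulation, 25 listeners, true preference 50%, 400,000 runs):

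| Judgments per listener | ICC 0.2 | ICC 0.3 | ICC 0.5 |
|---|---|---|---|
| 2 | 5.2% | 6.3% | 8.3% |
| 4 | 9.7% | 12.7% | 18.6% |
| 6 | 14.9% | 19.7% | 27.9% |
| 8 | 18.7% | 24.5% | 33.5% |

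With independent choices the size of this exact test is 3.3% to 4.1% for these values of m. For m from 4 to 8 the error is thus about 10% to 33%. For m = 2 it is close to nominal unless the correlation is high.

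**Step 4: one result per listener.** An exact sign test on 25 listener-level results keeps the two-sided level at 4.3%, and has 89% power if the true preference is 80%. Using the listener as the unit leaves a usable analysis.

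**The case against.** The strongest reply is that the text is incomplete rather than wrong, and much of that stands.

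- **Pooling is not written.** The sentence on booth and outside follows the sentence on the tally, so a separate tally in each setting is not excluded. A reader might infer that the plan adds the two settings. That is the natural reading, because only one overall result is named, but it remains an inference.
- **Independence is not claimed.** A reader might infer that the plan has a false-positive rate of 10% to 33%. It does not, because no test is specified. Those figures belong to a hypothetical test under assumed inputs.
- **A listener-level score is possible.** The 0 to 2 range in 3.3.2 fits a score for one listener over the two pairings that involve each sample. The live tally could be built the same way.
- **The settings are not described.** A reader might picture a quiet booth and uncontrolled noise outside. The documents characterise neither, and have no rule for reporting a tie.
- **The two harms partly offset each other.** Listeners who reverse preference between settings have low or negative correlation across settings, which reduces the inflation in step 3. With equal numbers of scored choices per listener, the pooled share also equals the mean of the listener shares, so the raw count loses correct precision rather than becoming biased. Unscored no-difference responses would make those weights unequal.
- **Overall preference is a declared interest.** Section 1.1 calls the study exploratory and refers to overall program preference. This is a secondary endpoint.

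The reply does not remove the gap. Even a per-listener tally hides a reversal if it is summed over both settings, and no reading of the text supplies a measure of uncertainty.

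**Conclusion.** The concern holds as a gap in the stated summary, not as a demonstrated analysis error. One overall tally is the only output named for a comparison made on several samples and in two environments. Nothing is planned by environment or by listener, and nothing separates preference from chance.

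That a single tally can mask a reversal is arithmetic. Whether a reversal will occur is unknown. The inflated error rate is conditional: it needs someone to test the raw count as independent, and its size rests on the assumed number of judgments and correlation.

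For a secondary endpoint of an exploratory study, this is a worthwhile and cheap improvement. It does not undermine the trial.

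**What to change.** Replace the tally in 3.3.3 with a participant-level analysis.

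1. For each participant and environment, compute net preference = (choices of Variation #4 − choices of Standard) / number of comparisons. Count a no-difference response as 0 and keep it in the denominator. The score runs from −1 to +1, and every listener has equal weight.
2. Report booth and outside separately, each with a participant-level Wilcoxon signed-rank test and a 95% confidence interval. State in advance how zeros and ties are handled, since scores based on few comparisons will produce many.
3. Describe results by sound sample, and state the number of samples per environment.
4. Compare the two environments within participant, labelled exploratory.
5. Base any overall statement on each participant's average over the two environments (n = 25), not on the raw count of choices.

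The cost is SAP wording and a little more analysis, with no new data, visits or participants. The intervals will be wider than a raw count of choices would suggest.

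### Speech-test equivalence is to be judged from averages alone, with no margin, interval or decision rule

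*Combined protocol and SAP*

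**What the plan says.** The speech-test analysis is stated in section 3.3.3: "For the speech test, average scores across all participants will be compared to determine equivalence". The only addition is that lower scores are better. The sentence does not say which averages are compared.

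The contrast has to be taken from elsewhere. Section 1.2 sets the secondary objective: "Determine if a proposed frequency response curves will impact speech intelligibility when compared to our current frequency response curves". Section 2.1.1 says that "SRT50 scores are recorded per condition tested (unaided, standard curve, and variation #4" are the measurements, and it lists the Standard curve and Variation #4 as the US Matrix test interventions. The natural reading is Variation #4 against Standard, within participant, because "The investigation consists of a single group of participants that will be tested in all conditions (cross-over" describes the design.

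On size, section 3.1 says "We will recruit 25 participants for all tasks" and reports 90% power at 5% alpha. It names no endpoint, test, effect size, SD or margin.

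**The concern.** To conclude equivalence is to say that any true difference is smaller than some amount that matters. That needs the amount (a margin) and a statement of precision (an interval or an equivalent test). The plan has neither. Two averages can lie close together because the curves perform alike, or by chance while a real difference exists, and the averages alone cannot separate the two. With no cut-off set in advance, any observed gap could be called equivalent or not after the results are seen.

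This is the only planned analysis that addresses the speech-intelligibility objective, and section 1.1 says the study will inform whether new gain curves go into products. A real SRT50 shift with Variation #4 could therefore be reported as equivalence. The streaming curves (Variations #1 to #3) and the primary endpoint are not affected.

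Sections 1.2 and 3.3.3 also pose different questions. The objective asks whether there is an impact, while the analysis section announces equivalence. They should be aligned.

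**Working it through.** **The plan's own figure.** Section 3.1 states that "the power analysis estimated the total sample size to be 25, leading to an actual power of 90" percent. This cannot be reproduced forward, because no effect size, SD, test or sidedness is given. Solving backwards for a paired t-test with n = 25, 5% alpha and 90% power gives a standardised paired difference of 0.676 (two-sided) or 0.603 (one-sided). The documents state neither value, so the figure is neither confirmed nor refuted, and it implies no equivalence margin.

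**Inputs.** n = 25 (section 3.1) and a paired comparison (section 2.1.1). The SD of the paired SRT50 difference is not given, so it is set to 1 and all results are in units of that SD. The standard error is 1/√25 = 0.2. Paired differences are assumed normal, with no dropout.

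**Step 1: precision.** Half-width = t(24) × 0.2, with the observed SD equal to 1.
- 95% CI: 2.064 × 0.2 = 0.413 SD
- 90% CI: 1.711 × 0.2 = 0.342 SD

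Even if the two averages were identical, the 95% CI would still allow a true difference of about 0.41 SD in either direction.

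**Step 2: averages only, with an assumed cut-off c.** Suppose the curves are called equivalent when the absolute mean difference is at most c. If the true difference equals c, the chance of that call is Φ(0) − Φ(−2c/0.2).

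| c (SD) | Called equivalent when true difference = c |
|---|---|
| 0.1 | 0.341 |
| 0.2 | 0.477 |
| 0.3 | 0.499 |
| 0.4 | 0.500 |

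TOST with margin c holds this probability at 5% or less.

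**Step 3: illustration only, non-significance read as equivalence.** The plan does not state this rule. With a two-sided 5% paired t-test (noncentral t, 24 df), the chance of a non-significant result is:

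| True shift (SD) | Not significant |
|---|---|
| 0.2 | 0.839 |
| 0.3 | 0.698 |
| 0.4 | 0.516 |
| 0.5 | 0.330 |

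**Step 4: what 25 participants could show with a margin M.** Equivalence is concluded if the 90% CI of the mean paired difference lies within ±M (TOST, 5% per side). Power at zero true difference comes from numerical integration over the sample SD. The last column is the n needed for 90% power.

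| M (SD) | Power, n = 25 | n for 90% |
|---|---|---|
| 0.3 | 2% | 122 |
| 0.4 | 25% | 70 |
| 0.5 | 57% | 45 |
| 0.6 | 80% | 32 |
| 0.7 | 92% | 24 |
| 1.0 | over 99% | 13 |

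At n = 25, 80% power needs M = 0.603 SD and 90% power needs M = 0.677 SD.

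**The case against.** The strongest reply is about weight. The study calls itself exploratory, the endpoint is secondary, the other planned analyses are simple tallies, and section 1.2 asks about impact rather than proof of equivalence. The word may be loose wording for checking that the averages look similar. That stands as a limit on severity. It does not remove the point, because section 3.3.3 announces an equivalence determination. If only description was meant, dropping the word costs nothing.

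The second reply concerns the numbers, and much of it stands:
- The cut-off in Step 2 is supplied here, and about 50% follows from any point-estimate threshold when the true difference sits on it.
- At margins of 0.1 or 0.2 SD, TOST keeps its error low only by almost never declaring equivalence: with n = 25 its power at zero true difference is below 0.01%.
- Step 3 describes a rule that the plan does not contain.
- None of the figures converts to an SRT50 shift without an SD.

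The firm statement is that a bare comparison of averages has no defined error rate. Steps 2 and 3 only illustrate how large the error could be.

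Thirdly, a mean difference with a 95% CI carries no decision rule either. That is so: it estimates the impact and does not give a yes-or-no answer. It is still a sound answer to the objective as worded, because it shows which differences the data allow.

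**Conclusion.** The concern holds and should be fixed. The stated method cannot support an equivalence conclusion for Variation #4 against Standard, and nothing elsewhere in the document supplies the missing margin, interval or rule. The 90% power in section 3.1 does not fill the gap.

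This is not a finding that 25 participants are too few. Whether they suffice depends on the margin, and the documents cannot settle that. The conclusion itself does not rest on any assumed SD. The sizes rest on normal paired differences, complete data on 25 participants, and Variation #4 minus Standard as the intended contrast, which is inferred from sections 1.2 and 2.1.1.

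**What to change.** Replace the sentence in section 3.3.3 with:

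> The mean within-participant SRT50 difference (Variation #4 minus Standard; positive values mean worse performance) will be reported with its 95% CI; unaided SRT50 is descriptive.

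This drops the equivalence wording, names the contrast, fits the objective in section 1.2 and needs no margin.

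If the sponsor wants to keep an equivalence claim, it should fix and justify a margin M in SRT50 units before data review. Equivalence is then concluded only if the 90% CI of the mean paired difference lies within ±M (TOST, 5% per side). The plan should note that n = 25 gives 90% power at zero true difference only if M is at least about 0.68 SD of the paired difference.

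The cost is SAP wording only, with the same participants, visits and data. The downsides apply only if the claim is kept: equivalence may be reported as not shown, and under two-sided TOST a benefit larger than M would also fail.
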